* Individuals at Increased Risk of HCV Infection	400	X	X
* Preselected Anti-HCV Positive	400	X	X
Alinity s Chagas			
* Individuals from Chagas Endemic Areas	600	X	
* Preselected T cruzi Parasite Positive	100	X	
* Preselected T cruzi Serology Positive	200	X	X

Demographic information including age, gender, and race are documented, where available. Risk factors, medical history, and supplemental results are documented, as applicable.

Confidential Information

This material is the property of Abbott Laboratories and must not be disclosed or used, except as authorized in writing by Abbott Laboratories.

2. Whole Blood Donor and Plasmapheresis Specimens

Plasma or serum specimens from unique blood donors and plasma specimens from unique plasmapheresis donors will be obtained.

Leftover specimens with sufficient residual volume of either plasma or serum specimen will be tested on each Alinity s blood screening assays as shown in the following table.

Assay	Whole Blood Donor (serum or EDTA plasma)*	Plasmapheresis Donor (source plasma)
HIV Ag/Ab Combo HBsAg/Confirmatory Anti-HCV	12,000	3,000
HTLV I/II Anti-HBc Chagas	15,000	NA

*At least one third of total whole blood donors will be EDTA plasma specimens and at least one third will be serum specimens.

No demographic information will be collected from these blood donors.

Inclusion and Exclusion Criteria

Random donor specimens selected for the study must have sufficient volume to complete designated testing. The Abbott monitor will provide the recommended volume requirements for each assay.

The subject/specimen must meet the following inclusion/exclusion criteria to be eligible for participation in this study:

Inclusion Criteria

Serum or EDTA plasma from a whole blood donor for each of the Alinity s assays or a plasmapheresis sample from a plasmapheresis donor (for HIV Ag/Ab Combo, HBsAg & Anti-HCV assays).

Exclusion Criteria

For testing with the Alinity s Chagas assay, exclude donors that have been screened on a previous donation using a licensed test for antibodies to *T cruzi*.

Note: A subject may participate at different times during the study for separate assay studies, but each subject should be represented only once for each assay.

Confidential Information

This material is the property of Abbott Laboratories and must not be disclosed or used, except as authorized in writing by Abbott Laboratories.

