Specimens should be shipped to Abbott Laboratories for additional testing or to a reference laboratory for supplemental testing as directed by the Abbott monitor. Store the specimens at -20 °C or below and ship overnight on dry ice. When shipped, specimens must be packaged and labeled in compliance with

Confidential Information

This material is the property of Abbott Laboratories and must not be disclosed or used, except as authorized in writing by Abbott Laboratories.

applicable state, federal, and international regulations governing the transport of clinical specimens and infectious substances.

A specimen may be removed from the study if the sample is found unacceptable for testing (e.g. inappropriate handling prior to testing, inadequate volume), or for other assignable causes. The reason for removal must be documented on an Incident CRF. Specimens removed from the study may need to be replaced, if deemed necessary by the Abbott monitor, to meet requirements for the minimum number of specimens.

B. General Study Procedures

1. Assay and/or System Configuration

The investigational Alinity s software is installed onto the Alinity s System at the time of instrument installation. The monitor will provide instructions on software configurations needed to start the study.

2. Instrument System General Procedures

Maintenance procedures are to be performed as instructed in the Investigational Alinity s System Operations Manual. Reports for maintenance and any documentation for component replacements that occurred during the study should be filed in study records.

The on-board inventory of the Alinity s System supplies and reagents will be checked daily. Load consumables and update inventory as necessary.

Refer to the Investigational Alinity s System Operations Manual.

3. Assay Calibration

Each Alinity s blood screening assay will be calibrated as described in the Alinity s Assay Clinical Brochure and the Alinity s Calibrator Clinical Brochure. The calibrator lot number and expiration date information will be read from barcodes when the material is tested on the instrument system. Refer to Calibration Procedures Section of the Alinity s System Operations Manual.

Calibration is to be performed for each investigational reagent lot. Print or transfer electronic report of the calibration and control results for each reagent lot tested. Refer to the Alinity s Assay Clinical Brochure and Alinity s Calibrator Clinical Brochure for frequency of calibration.

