- 5) If the quality control value still does not meet the validity criteria, place **new**

Confidential Information

This material is the property of Abbott Laboratories and must not be disclosed or used, except as authorized in writing by Abbott Laboratories.

Page 17 of 34

reagents on the instrument, **repeat assay calibration**, and **repeat all quality control testing**. If the controls are within the validity criteria, testing may continue.

Do not discard any reagents, calibrators, or controls that may have caused the out of range results.

- 6) If the quality control value still does not meet the validity criteria, contact the Abbott monitor for further instruction. Any test results generated since the last acceptable control run must be evaluated to determine if test results may have been adversely affected.

An Incident CRF must be completed, documenting the troubleshooting steps performed and any additional action required for resolution (e.g., recalibration, opening a new control bottle). The Abbott monitor must be notified when control failures are observed.

7. Method for Handling Retests and Error Codes

The following conditions may require retesting:

- Specimens with S/CO values ≥ 1.00 are considered initially reactive for all Alinity s and comparator assays. Specimens with S/CO values from 0.80 to < 1.00 are considered initially gray zone negative for all Alinity s assays. Initially reactive and initially gray zone negative specimens must be retested in duplicate.
- Testing of a specimen may be repeated if assignable cause (e.g., operator error, instrument malfunction) can be determined and documented by the site.
- For tests that cannot be completed and result in an **error code**, the test is to be repeated. If unable to retest the specimen or additional troubleshooting steps are required to resolve the error, an Incident CRF should be completed. A copy of the error report or screen display should be printed or electronically transferred, when possible.

The original SID will be used for all repeat testing. Refer to the Specimen Collection and Preparation for Analysis Section of the Alinity s Assay Clinical Brochure. If re-centrifugation is required, document on the appropriate CRF.

8. Additional Troubleshooting

The Abbott monitor may request certain procedures or additional testing to be performed for troubleshooting purposes. The additional testing may require various procedures be repeated.

Confidential Information

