- 2) Refer to the “Specimen Collection and Preparation for Analysis” section of the clinical brochure for detailed procedures on handling of samples prior to placing specimens on the Alinity s System.

Confidential Information

This material is the property of Abbott Laboratories and must not be disclosed or used, except as authorized in writing by Abbott Laboratories.

- 3) A single replicate of each specimen should be tested with the investigational Alinity s assay. Specimens should be placed in barcoded tubes in a sample rack and placed on the Alinity s System to schedule testing.
- 4) Schedule a Alinity s release control for each assay. If release control is not already on the system, place the calibrator and control rack on the Alinity s System in the priority bay to schedule testing.

Note: All testing data generated before the release control will be printed when release control testing is complete.

- 5) Specimens with an initial S/CO result of ≥ 1.00 are considered initially reactive. Specimens with an initial S/CO result ≥ 0.80 to < 1.00 are considered initially gray zone negative. Both initially reactive and initially gray zone negative specimens should be retested in duplicate with the Alinity s method. Specimens with an initial S/CO results of < 0.80 are considered nonreactive and do not require further testing.
- 6) Repeat testing should be performed using the same reagent lot and be done on the same day or the following workday. If greater than 48 hours has elapsed from initial centrifugation, re-centrifuge the sample and document on the Incident CRF. Refer to Alinity s assay clinical brochure for further information regarding centrifugation of specimens.
- 7) If both duplicate retest results are nonreactive ($S/CO < 0.80$), then the specimen is considered negative and no further testing is required. If either retest result has $S/CO \geq 0.80$, then supplemental testing for the assay will be performed.
- 8) Each specimen should be tested with the comparator PRISM method. Specimens initially reactive by the comparator method should be retested in duplicate on the same day or on the next work day of testing. If re-centrifugation is required for the comparator method testing, document on the appropriate CRF. Refer to comparator package insert for further information regarding centrifugation of specimens.
- 9) If the comparator method result is repeatedly reactive, then supplemental testing for the assay will be performed.

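### Removal of donor specimens for inadequate volume is not confined to the time before the first result, which could slightly inflate specificity

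*Combined protocol and SAP*

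**What the plan says.** Donor specimens are residual material. Section VI.A.2 sets a volume condition at selection: "Random donor specimens selected for the study must have sufficient volume to complete designated testing". The amount is left to the sponsor: "The Abbott monitor will provide the recommended volume requirements for each assay". The text does not say whether it includes retest and supplemental volume.

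Section VI.A.3 then gives a removal rule: "A specimen may be removed from the study if the sample is found unacceptable for testing (e.g. inappropriate handling prior to testing, inadequate volume". A reason is required ("The reason for removal must be documented on an Incident CRF"), and replacement is discretionary: "Specimens removed from the study may need to be replaced, if deemed necessary by the Abbott monitor". The rule does not state a time limit or require that the result be unknown.

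Section VI.B.7 makes further testing mandatory after some results: "Initially reactive and initially gray zone negative specimens must be retested in duplicate". Section VI.C.2 repeats this in step 5, ends testing for specimens below 0.80 S/CO, and in step 7 sends any specimen with a retest at or above 0.80 to supplemental testing. Steps 8 and 9 impose a duplicate retest and supplemental testing on PRISM-reactive specimens.

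Section IX.B.2.c calculates specificity as F/(C+F), or F/(C+B+F) with repeatedly reactive indeterminates added. Both need a final status.

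**The concern.** A donor that is clearly nonreactive on both assays needs the least volume, and a reactive donor needs the most. If volume can be found inadequate after the first result is known, shortfalls will fall more often on reactive specimens, and each replacement is very likely to be nonreactive. Donor specificity rests on few events, so losing a handful of false repeatedly reactive specimens moves the estimate, and it moves upward. The plan also has no rule for a repeatedly reactive donor whose supplemental testing cannot be completed. Such a donor has no clear cell in the final-status table, even without formal removal.

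**Working it through.** **1. Volume needed, by result (VI.B.7; VI.C.2 steps 3 to 9)**

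- Alinity s below 0.80 and PRISM nonreactive: one Alinity s replicate plus the PRISM test.
- Alinity s at or above 0.80: two more Alinity s replicates. If either is at or above 0.80, supplemental assays follow.
- PRISM initially reactive: two more PRISM replicates. If repeatedly reactive, supplemental assays follow.

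**2. Sharing of specimens (III.A).** Six assays × 15,000 = 90,000 donor-assay results. With about 23,000 donors, the low end of the stated range, that is 90,000 / 23,000 ≈ 3.9 assays per donor. Running short is therefore plausible. The documents do not say how often.

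**3. Existing back-up routes (III.F).** Follow-up is triggered by disagreement with final status after supplemental testing. A donor that never reached a final status has not met that trigger. Testing the index plasma unit is optional.

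**4. The plan's own figure.** 12,000 + 3,000 = 15,000 reproduces the donor total for three assays. The power basis in IX.B.2.d (80%, α ≤ 0.05) cannot be reproduced, because no null or target specificity is given. The documents thus give no acceptance limit against which to judge a shift.

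**5. Illustration.** Assumptions not in the documents: N = 15,000 negative-status donors; x = 15 false repeatedly reactives; k of them lost and replaced by nonreactive donors. Specificity = 1 − (x − k)/N, and the shift is k/N. For y remaining false reactives, the exact 95% limits for y/N are the Beta quantiles B(0.025; y, N−y+1) and B(0.975; y+1, N−y), each subtracted from 1.

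- k = 0: 1 − 15/15,000 = 99.900% (99.835 to 99.944).
- k = 3: 1 − 12/15,000 = 99.920% (99.860 to 99.959); shift 0.020 points.
- k = 5: 1 − 10/15,000 = 99.933% (99.877 to 99.968); shift 0.033 points.

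If three drop out without replacement, 14,985 / (14,985 + 12) = 99.920%, the same to three decimals.

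**6. Range over assumed rates, N = 15,000 (counts rounded)**

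| False repeatedly reactives | 20% lost | 50% lost | All lost |
|---|---|---|---|
| 8 (0.05%) | +0.013 | +0.027 | +0.053 |
| 15 (0.10%) | +0.020 | +0.053 | +0.100 |
| 30 (0.20%) | +0.040 | +0.100 | +0.200 |
| 75 (0.50%) | +0.100 | +0.253 | +0.500 |

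Entries are percentage points. The shift cannot exceed the false repeatedly reactive rate.

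**7. Smaller stratum.** Specificity is also reported by specimen type. Among 3,000 plasmapheresis donors with an assumed 3 false reactives, losing 2 moves 99.900% (99.708 to 99.979) to 99.967% (99.814 to 99.999).

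**8. Losses that do not matter.** An initially reactive donor that would have retested nonreactive belongs in F. Losing one without replacement gives 14,984 / (14,984 + 15) = 99.900%, no visible change. The same holds for Alinity s specificity when an Alinity s-nonreactive, PRISM-reactive donor is lost, although comparator specificity is then exposed. Removal unrelated to the result leaves expected specificity unchanged.

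**The case against.** A reader might infer that the eligibility criterion in VI.A.2 itself selects on the result. It does not. It is a uniform check at selection, and because retesting is mandatory, the volume it asks for may well cover the full sequence. The monitor's volume instructions are not among the documents. If they reserve that volume for every donor, most of the risk disappears.

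A reader might also infer that only Alinity s-reactive donors can be lost this way. That is too strong: PRISM-driven retests, error-code repeats and multi-assay use consume volume from Alinity s-nonreactive donors too. Nor does the Incident CRF instruction in VI.B.7 for specimens that cannot be retested govern reactive donors; it sits under error codes.

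The removal rule can fairly be read as covering unsuitability found before testing. Section IX.A does not list volume among its causes for exclusion from analysis. Removals need a documented reason, excluded data are listed with reasons, and the use of every result is summarized.

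What stands of this: the safeguards make removals visible but neither prevent them nor say how to count the donor. Only the handling example in VI.A.3 carries a timing qualifier; inadequate volume does not. Volume is a ground for removal in VI.A.3 but not for exclusion in IX.A, which itself needs clarifying. The monitor who decides on replacement also reviews all test results.

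**Conclusion.** The gap is real and its likely direction is upward, but its size is unknown and probably small. Under the assumed 15 false reactives in 15,000, losing 3 to 5 raises specificity by 0.020 to 0.033 points. Both shifted estimates lie inside the interval obtained with no loss (99.835 to 99.944). The false-reactive rate, the share lost and replacement by nonreactive donors are all assumptions. The documents do not support a statement that specificity is inflated, only that the rules as written permit it. The point deserves action because the remedy is cheap and the loss would act mainly on the few events that determine the endpoint.

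**What to change.** - **VI.A.2:** state that sufficient volume covers the initial Alinity s test, duplicate retest, comparator testing and supplemental testing for every donor, and that it is checked and recorded before the first result.
- **VI.A.3:** allow removal or replacement for inadequate volume only before any Alinity s or PRISM result exists.
- **IX.B.2.c:** keep later shortfalls in the dataset and tabulate them by initial result. Add a prespecified sensitivity analysis, for Alinity s and comparator, that counts donors with unresolved reactive results as false positives unless NAT, follow-up or the index plasma unit resolves them.

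The last item should remain a sensitivity analysis. Counting an unretested initial reactive as repeatedly reactive in the primary analysis would conflict with the retest-based classification in VI.C.2, and placing every unresolved repeatedly reactive donor in cell C could label a true infection as a false positive.

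The cost is a few sentences, one check at selection and one extra table. A few more donors may be rejected at selection, and reported specificity may be slightly lower. The planned number of donors does not change.

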At the conclusion of the study, a copy of the completed CRF will be maintained at each investigational site.

C. Supplemental Data Transfer

Confidential Information

This material is the property of Abbott Laboratories and must not be disclosed or used, except as authorized in writing by Abbott Laboratories.

Page 22 of 34

The HIV, HBV and HCV nucleic acid testing (NAT) results for the donor specimens will be provided to Abbott in a format as agreed upon with the clinical monitor.

The results for supplemental testing will be entered or a copy of the results (e.g., instrument printout, worksheet, report) will be uploaded into the eCRF system by the site.

VIII. Adverse Events

No side effects or adverse events are anticipated. In the unexpected event of a serious adverse event resulting from use of the investigational device, the Abbott monitor must be notified immediately by telephone and subsequently in writing within five (5) days of the occurrence. The event must be described on the adverse event case report form, as applicable. All adverse events are to be followed to satisfactory resolution, and any measures taken, as well as the follow-up, reported on the appropriate CRF.

A. Device Adverse Events

A **Device Adverse Event** is any effect on the health or safety of an individual associated with the use of a product which has or may have caused or contributed to an injury, a system malfunction or user error resulting in personal injury (e.g., electrical shocks, burns), or exposure to potentially hazardous material (e.g., chemical or biohazardous), or a fire or visible smoke that was not self-contained to the system and caused damage outside of the system.

A **Device Serious Adverse Event** is an adverse event that has or may have caused or contributed to a death or serious injury of an individual or an adverse event resulting from malfunction that could cause or contribute to a death or serious injury if the malfunction were to recur. A serious injury includes a life-threatening illness or injury, an illness or injury which results in permanent impairment of a body function or permanent, irreversible damage to body structure, or a condition, an injury or illness necessitating a medical or surgical intervention by a health care professional to prevent permanent, irreversible impairment of a body function, or damage to a body structure.

B. Subject Adverse Event

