Donor specimens used in the study are collected as part of the routine blood donation process. Events related to the blood or plasma donation process will be handled according to the donor center procedures and not recorded in the study files.

For donor follow-up specimens collected under this protocol, subject adverse events will be documented if they occur. It is expected that drawing blood or plasma may cause pain, bruising, lightheadedness, and on rare occasion, infection

Confidential Information

This material is the property of Abbott Laboratories and must not be disclosed or used, except as authorized in writing by Abbott Laboratories.

Page 23 of 34

at the site of the blood draw. These events will not be recorded as adverse events as they are considered to be normal events that may occur during the course of a blood or plasma draw. Other events that may occur such as fainting, that are not routinely associated with a blood or plasma draw, must be recorded on the Subject Adverse Event Case Report Form and be followed to satisfactory resolution.

A **Subject Adverse Event** is any unfavorable or undesirable medical occurrence (e.g., sign, symptom, or disease) temporally associated with the specimen collection procedure performed.

A **Subject Serious Adverse Event** is an untoward medical occurrence that:

- results in death
- is life-threatening
- requires inpatient hospitalization or prolongation of existing hospitalization
- results in persistent or significant disability/incapacity, or
- results in a congenital anomaly/birth defect.

IX. Statistical Procedures

A. General Information

All data analyses will be performed, and tables and listings of data will be provided by ADD Statistics using SAS version 9.2 or higher.

If revised or additional analyses are required, a description of the additional or revised analyses and justifications for the changes will be documented and approved by the same functional areas as the original approvers to the protocol.

The Abbott monitor will review all test results and may request that certain observations be excluded from analysis if there is an assignable cause, i.e., control or validity criteria failure, instrument errors or problems, acknowledged technologist error, and/or noncompliance with the study protocol. All results tested according to the protocol and not excluded will be eligible for analysis.

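### Section VIII.B exempts draw-site infection and other listed follow-up draw events from recording with no exception for serious events, which conflicts with its own serious adverse event definition

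*Combined protocol and SAP*

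**What the plan says.** Section VIII.B leaves events of the routine donation to the donor center's procedures. For the extra draw it sets a general rule: "For donor follow-up specimens collected under this protocol, subject adverse events will be documented if they occur".

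It then names what a draw is expected to cause: "pain, bruising, lightheadedness, and on rare occasion, infection", the last of these at the site of the draw. Of this list it says: "These events will not be recorded as adverse events as they are considered to be normal events". The contrasting rule follows: "Other events that may occur such as fainting, that are not routinely associated with a blood or plasma draw, must be recorded". A dedicated form for subject adverse events is named for this purpose.

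Two definitions close the section. The first, of a Subject Adverse Event, is broad: it "is any unfavorable or undesirable medical occurrence (e.g., sign, symptom, or disease) temporally associated with the specimen collection procedure performed". The second, of a Subject Serious Adverse Event, is set by outcome, and one of its criteria is an event that "requires inpatient hospitalization or prolongation of existing hospitalization". That definition carries no instruction on recording, notification or timing.

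The opening paragraph of Section VIII does have a notification rule, with immediate telephone contact and a written report within five days. It begins: "In the unexpected event of a serious adverse event resulting from use of the investigational device". The same paragraph asks that all adverse events be followed to resolution and reported on a form.

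**The concern.** The exemption works by type of event, and the serious definition works by outcome. An event can fall under both, and the section does not say which prevails. Draw-site infection is the listed event for which this matters most. Pain, bruising or lightheadedness would rarely meet a serious criterion.

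Index donor specimens are residual material from routine donation. The follow-up draw of about 20 to 60 mL, taken under a separate research consent (Sections III.A and III.F), is the one physical procedure that this protocol adds for donors, and Section VIII.B is the subject-safety record for it. If a site applies the exemption as worded, a serious event from that procedure could be missing from the record. The stake is the completeness of safety recording. Sensitivity, specificity and reproducibility are not involved.

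**Working it through.** The main check is textual. Take one case: a donor gives a follow-up specimen, develops an infection at the draw site and is admitted to hospital. Apply each rule in turn.

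1. **Subject Adverse Event definition (VIII.B).** The infection is an unfavorable occurrence temporally associated with the collection, so it qualifies.
2. **General documentation rule (VIII.B).** Such events "subject adverse events will be documented if they occur", so the case should be recorded.
3. **Exemption (VIII.B).** Infection at the draw site is on the list. No limit by severity, outcome or seriousness is attached, so the case should not be recorded.
4. **Rule for other events (VIII.B).** This covers events outside the list that are not routine for a draw. Draw-site infection is on the list, so on its face the rule does not apply.
5. **Subject Serious Adverse Event definition (VIII.B).** Admission meets it. The definition does not exclude listed events, but it neither overrides step 3 nor triggers any action.
6. **Notification rule (opening of VIII).** It is worded for events resulting from use of the investigational device. A venipuncture is not use of the assay or analyzer, so the rule does not clearly reach the case.
7. **Follow to resolution (opening of VIII).** It applies to adverse events, but step 3 says that listed events are not recorded as such.
8. **Incident form (X.E).** It covers unplanned or unexpected events. VIII.B describes the listed events as expected, so this route is uncertain.

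Steps 2 and 3 give opposite answers for the same case, and no later step clearly settles which one governs. The grounds for exemption also sit awkwardly with infection: the section calls the listed events normal, yet expects infection only rarely, while fainting must be recorded.

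**How many donors could be exposed.** The documents state neither the number of follow-up draws nor an expected specificity, so a range must be assumed.

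- Donor specimens per assay: 15,000 (Sections III.A and VI.C.2). Assays with donor testing: six (table in VI.A.2, counting HBsAg and its confirmatory assay as one).
- Follow-up is sought when the investigational result disagrees with final status (III.F). Among donors, treated in IX.B.2 as a presumed zero-prevalence population, this is approximated by false reactives: 15,000 × (1 − specificity).

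| Assumed specificity | Discordant donors per assay | Summed over six assays |
|---|---|---|
| 99.5% | 15,000 × 0.005 = 75 | 450 |
| 99.9% | 15,000 × 0.001 = 15 | 90 |
| 99.99% | 15,000 × 0.0001 = 1.5 | 9 |

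These are discordant donors, not draws. Section III.F promises only an attempt to obtain a specimen, and III.B says that the donor may be asked. Actual draws would be fewer. Serious infections among them would be fewer still, and the documents give no basis for estimating that number.

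**The case against.** A reader might infer that the protocol orders serious events to be left out, or that such an event would certainly go unrecorded. The documents do not support that. The exemption gives its own reason, that the listed events are normal for a draw, and it covers infection only at the draw site. An admission is hard to call normal, and an infection that has spread is arguably no longer at the site. A reasonable site could treat either as an other event and record it. The general documentation sentence points the same way, and a serious definition would have little purpose if serious events were never meant to be captured. The incident form might also catch an admission. Form instructions (VII.B) and the GCP-aligned list of investigator requirements (X.A) are not part of the documents and may help. All of this stands. It makes the text ambiguous, but none of it resolves the conflict.

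Two other inferences go too far. One is that infection is the only potentially serious expected harm of the draw: the protocol does not rank the listed events by potential seriousness. The other is that a single count, such as 90 donors, measures the risk: it rests on one assumed specificity and counts discordant donors instead of draws.

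It is also fair to say that leaving minor, expected draw effects unrecorded is a legitimate design choice. The point here does not dispute it.

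**Conclusion.** The point holds as an internal conflict in Section VIII.B. With no stated exception for seriousness, an event can meet the section's own serious definition and be exempt from recording, and the only serious-event notification rule is tied to the device. What a site would actually do is uncertain, so the finding is that the wording permits omission, not that it requires it.

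The practical size is small. Under the assumed specificity range, about 75 to 1.5 donors per assay would be discordant, fewer would be drawn, and only rare events among those would be affected. No performance estimate changes. The change is still worth making, because the gap concerns serious events from the one procedure added for donors and costs little to close. The conclusion rests on the visible text. Form instructions or site guidance outside the documents could narrow the gap.

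**What to change.** Reconcile the passages in Section VIII with three statements:

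1. The exemption for normal draw events does not apply to any event that meets the section's own Subject Serious Adverse Event definition.
2. Such events are recorded on the existing Subject Adverse Event form.
3. Whether the notification rule at the start of Section VIII, now worded for the investigational device, also covers serious events from the follow-up draw.

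The third statement is needed because amending VIII.B alone would leave these events recorded but without a clear notification instruction. The form already exists and the exemption for minor effects can stay. The cost is a few sentences at the next amendment and an occasional extra form. The analysis and sample size are untouched.
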